# 8 Participant selection

Participants are eligible for the trial if they meet all of the following inclusion criteria and none of the exclusion criteria apply. All queries about participant eligibility should be directed to the Trial Manager before registration.

#### 8.1 Inclusion criteria

- Diagnosis of HD, confirmed by genetic testing
- Above the age of 18
- A participant (current or newly enrolled) in the Enroll-HD study
- Up to and including stage 2 disease status (TFC 7-13), but participants must have a diagnostic confidence of 4.

#### 8.2 Exclusion criteria

- · Diagnosis of juvenile onset HD
- History of co-morbid neurological conditions such as multiple sclerosis or stroke
- · Acute orthopaedic conditions (within a month) e.g. ankle sprain or fracture
- Inability or unwillingness of participant or legal guardian to give written informed consent

# 9 Recruitment, Screening, Registration and Randomisation

# 9.1 Participant identification and pre-screening

Participants will be identified from registered Enroll-HD participants at each site. If an individual is deemed suitable for PACE-HD and not yet recruited to Enroll, they could be recruited onto Enroll-HD at that time however must be enrolled on Enroll-HD prior to randomisation. Enroll-HD is a global research platform that has at its core a worldwide observational study for Huntington's disease families(https://www.enroll-hd.org/learn/about-this-study/). Enroll-HD monitors the onset of the disease and its progression in different people and open to the following categories: gene carriers, gene negative and family controls.

One of the optional components within the Enroll-HD study is the request to give permission to be contacted to receive information about other additional and affiliated HD research projects. In consenting to participate in the Enroll-HD study, participants also give their permission for their coded data to be made available to any researchers with a legitimate research project who wants to better understand HD. Only coded clinical data are shared with the researchers therefore, the risk that identifying information will be accidentally disclosed is low.

Participants registered on Enroll-HD at participating sites will be reviewed for eligibility (pre-screening) for inclusion in the trial by Enroll-HD research staff. A list will be generated prior to the start of recruitment of ENROLL-HD participants that satisfy the inclusion criteria at each site. A list of all ENROLL participants and the generated lists of potentially eligible participants will be sent to the PACE-HD trial manager prior to the start of recruitment and will be updated every quarter. The trial manager will use the list of potentially eligible participant to pre-populate screening logs to be sent to individual sites. Sites will be asked to cross reference potentially eligible participants in the screening log with their own records to assess eligibility against the exclusion criteria. Those that fit the inclusion criteria and none of the exclusion criteria will be sent an invitation to participate in the trial by the local research team prior to or at their next Enroll-HD visit, provided that in Enroll-HD the participants have consented to be contacted between trial visits to receive information about HD research studies. All interested potential participants will be given as long as they need to read the material and discuss with their

families and carers before being asked to make any decisions. Participants will have the opportunity to ask any questions they have about the trial and discuss their potential involvement before providing informed consent.

# 9.2 Screening logs

A log of all potentially eligible participants (as defined by the trial inclusion criteria) at each site will be held. This will be pre-populated by the PACE-HD trial manager with information obtained via the ENROLL-HD co-ordinator (see section 9.1) A record of any potentially eligible participants meeting exclusion criteria and thus deemed ineligible will be recorded in the screening log. The log will contain a record of all those approached to take part in the trial and subsequently declined to participate, were excluded from participation following a screening assessment or were enrolled in the trial. Reasons for not participating will be recorded. When at site, logs may contain identifiable information, but this **must** be redacted prior to being sent to the CTR.

The screening log should be sent to [contact] monthly (see section 19 for further detail on data monitoring/quality assurance).

All pre-screening (conducted as part of the process of participant identification) and screening information will be recorded centrally to inform the trial CONSORT diagram (Appendix I).

#### 9.3 Recruitment rates

A total of 120 participants will be recruited into the prospective observational cohort at 6 sites. Recruitment is expected to take approximately 15 months, with a target of 1-2 participants a month.

# 9.4 Informed consent

Consent may be taken by qualified researchers or clinicians at each site, details of which will be recorded on the delegation log at the site. Please note, only when written informed consent has been obtained from the participant and they have been randomised/enrolled into the trial can they be considered a trial participant. Participants should always be asked to sign a consent form before conducting any trial mandated procedures. One copy should be given to the participant but the original copy should be kept in the investigator site file.

The right of the subject to refuse to participate in the trial without giving reasons must be respected. After the participant has entered the trial, the investigator must remain free to give alternative treatment to that specified in the protocol, at any stage, if he/she feels it to be in the best interest of the participant. However, the reason for doing so should be recorded and the participant will remain within the trial for the purpose of follow up and data analysis according to the treatment option to which he/she has been allocated. Similarly, the participant must remain free to withdraw at any time from the protocol treatment without giving reasons and without prejudicing his/her further treatment.

# 9.5 Registration and Randomisation

# 9.5.1 Registration

Potential participants will be screened for eligibility by local site teams as described in section 9.1. Those meeting eligibility criteria and providing informed consent will be registered as a trial participant and assigned a unique trial identification number prior to baseline data collection. At sites conducting the nested RCT, the participant will then undergo a further safety assessment to determine their ability to take part safely in the interventional trial prior to baseline data collection. Only those passing the safety screening assessment will be eligible for randomisation. The Malnutrition Universal Screening Tool' ('MUST') for adults will be completed at baseline for those in the intervention sites.

#### 9.5.2 Randomisation

The randomisation will be stratified by country. Participants within intervention countries will be randomised in a 1:1 ratio to receive the intervention or continue with their current regime of physical activity. A minimisation technique will be used for randomisation to ensure a similar distribution of selected participant factors between trial groups. The first participant is truly randomly allocated; for each subsequent participant, the treatment allocation that minimises the imbalance on the selected factors between groups at that time is selected. That allocation may then be used, or a choice may be made at random with a heavy weighting in favour of the intervention that would minimise imbalance (for example, with a probability of 0.8). The participant factors to be balanced in the nested RCT will be age (above or below age 50 years), gender and motor impairment (above or below UHDRS total motor score 40). The randomisation process will be automated via the PACE-HD database.

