#### 14 Statistical considerations

#### 14.1 Randomisation

A minimisation technique will be used for randomisation to allow for balancing of age (above or below age 50 years) and motor impairment (above or below UHDRS total motor score 40) at baseline. The randomisation will be stratified by country. A Randomisation schedule will outline all randomisation procedures, implementation and back-up system.

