#### 14.2 Blinding

There will be no blinding of participants or assessors in the nested RCT. The nature of the intervention means that participants cannot be blinded however there are a range of quantitative outcomes that will be collected in an attempt to minimise bias.

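### Section 9.5.2 leaves open a minimisation rule with no random element after the first participant, which in this unblinded RCT could make allocation guessable

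*Protocol*

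**What the plan says.** Section 9.5.2 states that "The randomisation will be stratified by country" and that minimisation will be used. It guarantees chance once: "The first participant is truly randomly allocated". For everyone after that, the arm that minimises imbalance is identified, and then "That allocation may then be used, or a choice may be made at random with a heavy weighting" towards that arm. The weighting appears only as an illustration, "for example, with a probability of 0.8". Allocation is automated through the trial database.

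The balancing factors in section 9.5.2 are "age (above or below age 50 years), gender and motor impairment (above or below UHDRS total motor score 40"). Section 14.1 gives a shorter list, "balancing of age (above or below age 50 years) and motor impairment (above or below UHDRS total motor score 40"), with no gender. It leaves procedures, implementation and back-up to a separate randomisation schedule, and says nothing for or against a random element.

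Section 14.2 states: "There will be no blinding of participants or assessors in the nested RCT". Section 12 (data collection and blinding) adds that site researchers, who may include the therapists delivering the intervention, collect assessments knowing the allocation. Consent is taken locally (section 9.4), and at RCT sites a safety assessment must be passed before randomisation (section 9.5.1).

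**The concern.** Minimisation without a random element makes most allocations a function of earlier allocations and the new participant's factors. Automation hides a list, but it does not stop anyone working out the next arm from the past ones. Several features make that practical here: earlier allocations are openly known at the site, the sequence within a country is short, and the factors are two or three yes/no items, partly available from Enroll-HD records before consent.

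Staff who expect a particular arm could, even without intent, approach, encourage or pass at the safety screen different kinds of people. Selection on motivation or frailty would bias the effect estimates, and adjusting for the balancing factors (section 15.1) would not remove it. It would also reach two primary measures in section 5.3: retention, defined by completing the intervention, and adherence, defined by intervention sessions completed. Both depend on who enters the intervention arm.

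**Working it through.** The protocol gives no predictability figure to reproduce, so the check is a simulation.

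**Inputs from the protocol.** RCT size 30 + 30 = 60 (section 6); three RCT sites (section 15.1); 1:1 allocation; three binary factors (section 9.5.2) or two (section 14.1); probability of taking the minimising arm 1.0 (deterministic option) or 0.8 (the protocol's example).

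**Assumptions.** One country per RCT site with 60 / 3 = 20 participants each; each factor at 50% prevalence; equal weights; ties broken at random. The protocol states neither the number of RCT countries nor their split.

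**Method.** For each new participant, the rule compares the total absolute marginal imbalance over that participant's factor levels under each arm, and favours the arm giving the smaller total. A site guesser always names the arm that the known tallies favour, and tosses a coin on ties. I ran 1,200 trials per scenario; 50% correct means unpredictable.

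With a full tally inside the country, the expected share of correct guesses is

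correct = p x (share not tied) + 0.5 x (share tied).

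- Deterministic: 74.7% of allocations are not tied, so 1.0 x 0.747 + 0.5 x 0.253 = 0.874. All of that 74.7% is certain in advance.
- At 0.8: 76.5% are not tied, so 0.8 x 0.765 + 0.5 x 0.235 = 0.730. None is certain.

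The simulated values are 87.3% and 73.2%. Scenarios for 3 x 20 and three factors:

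| Minimisation and what the guesser uses | Deterministic | 0.8 |
|---|---|---|
| Within country, all factors tallied | 87% | 73% |
| Within country, motor score not known | 80% | 69% |
| Within country, count of arms only | 71% | 64% |
| Country as a factor in one pooled scheme, own-country full tally | 67% | 62% |
| Same pooled scheme, own-country count of arms only | 68% | 61% |

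**Sensitivity.** With the two factors of section 14.1, the full within-country tally gives 85% and 71%. Two countries of 30 give 88% and 73%. Summing signed instead of absolute differences moves the two-country, three-factor figures to 89% and 75%. Factor prevalences between 0.2 and 0.6 make almost no difference.

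**Price in balance.** The mean absolute difference in arm size per country at the end (3 x 20, three factors, within country) is 0.28 if deterministic and 0.97 at 0.8, or about 0.3 and 1.0 participants. A probability of 0.7 gives 66% correct guesses and an imbalance of about 1.5.

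**The case against.** The best defence is that section 9.5.2 describes minimisation generically and adopts neither variant. Section 14.1 sends the operating detail to a randomisation schedule, which may well specify a random element. That stands as far as it goes: the text shows a permission, not a choice. It does not dispose of the point, because a schedule with no random element would comply fully with the protocol.

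The upper figure also favours the guesser. It needs separate minimisation in each country and staff who know the algorithm, tally every margin and know the new participant's factors. The motor score may not be available: it is a baseline measure, registration precedes baseline data collection, and newly enrolled Enroll-HD participants are eligible. Reading stratification as separate schemes per country is natural, but not certain. A deterministic pooled scheme (67%) is less guessable from one country than a within-country scheme with the 0.8 weighting (73%). These points are sound, and are why the result is a range.

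Screening logs, pre-populated by the trial manager and returned monthly with reasons for non-participation (sections 9.1 and 9.2), make selective approach auditable. They do not prevent it.

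Finally, effects are exploratory and no formal hypothesis tests are planned (section 14.3). That limits the damage from bias, but section 5.3 retention and adherence remain exposed.

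**Conclusion.** The point holds as a defect of wording: two materially different allocation methods are authorised, and the weaker one is not excluded. If the deterministic option is used, informed site staff would guess about 67-87% of allocations under the 3 x 20 assumption, against about 61-73% with a 0.8 random element. In the within-country case, about three quarters of allocations would be fully determined in advance, against none. The position within each range turns on the number and size of countries, within-country or pooled minimisation, and how much staff tally.

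Three stronger readings are tempting and not supported. First, a reader might infer that allocation in this trial is deterministic; the protocol only allows it, and the schedule is not shown. Second, a reader might take 87% as the expected predictability; it is near the favourable end for the guesser. Third, a reader might infer that steering participants between arms directly drives the progression decision. Section 15.1 sets that rule on drop-out from the RCT, without separating the arms.

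The differing factor lists in sections 9.5.2 and 14.1 are a plain inconsistency, whichever allocation rule was used.

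**What to change.** - In section 9.5.2, remove the half of the sentence that lets the minimising arm be assigned outright, so that only the weighted random choice remains. State that every allocation after the first includes a random element.
- Fix the probability in the restricted randomisation schedule and take the example value out of the protocol, which sites hold. The value is a trade-off between concealment and balance; 0.8 is one reasonable choice.
- State whether minimisation runs separately within each country or with country as a factor in one scheme.
- Give the same factor list in sections 9.5.2 and 14.1, settling whether gender is included. Section 15.1 adjusts for these factors, so the analysis depends on the answer.
- In the trial report, state the method, probability and factors actually used. If no random element was used, say so as a limitation on concealment.

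The cost is a few sentences and, if needed, a database setting. Balance within country becomes slightly looser, by about 0.7 participants per country on average (1.0 - 0.3) at a probability of 0.8 under the 3 x 20 assumption.

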# 10 Withdrawal & loss to follow-up

#### 10.1 Withdrawal

Participants have the right to withdraw consent for participation in any aspect of the trial at any time. The participants care will not be affected at any time by declining to participate or withdrawing from the trial.

If a participant initially consents but subsequently withdraws from the trial, clear distinction must be made as to what aspect of the trial the participant is withdrawing from. These aspects could be:

- 1. Withdrawal from trial intervention
- 2. Partial withdrawal from further data collection (e.g. some of sample collection, questionnaires, clinical assessments)
- 3. Complete withdrawal from further data collection
- 4. Withdrawal of permission to use data already collected

The withdrawal of participant consent shall not affect the trial activities already carried out and the use of data collected prior to participant withdrawal, unless specifically stated by the participant.

It may be important to collect safety data if there is an ongoing safety related event at the time of withdrawal, especially if the participant withdraws because of said safety event. There is specific guidance on this contained in the Participant Information Sheet but briefly:

If a participant does wish to stop taking part in the trial completely, we may ask if they are willing to be seen one last time for an assessment. This assessment would not be for the purposes of collecting research data, but would be a clinical review of the ongoing safety issue to ensure that a resolution had been reached or appropriate clinical management of the issue be put in place for the participant.

A participant may withdraw or be withdrawn from trial intervention for the following reasons:

- Withdrawal of consent for treatment by the participant
- Any alteration in the participant's condition which justifies the discontinuation of the intervention in the Investigator's opinion (such as significantly increased falls or a significant deterioration in the participant's health status [including deterioration in mental state]).

In all instances participants who consent and subsequently withdraw should complete a withdrawal form (see Withdrawal Form in trial pack) or the withdrawal eCRF in the trial database should be completed on the participant's behalf by the researcher/clinician based on information provided by the participant. Withdrawal forms completed by the participant should be sent to

[contact] . Any queries relating to potential withdrawal of a participant should be forwarded by email to: [contact].

#### 10.2 Loss to follow up

For the longitudinal observation study we do not anticipate a high rate of loss to follow up due the participant's ongoing involvement in Enroll-HD. We will adhere to the Enroll-HD protocol for managing lost to follow up participants in the observational cohort.

For participants in the nested RCT, participants will be deemed to be lost to follow up if they fail to attend more than 4 consecutive coaching contact sessions.

As this is a pragmatic trial, if a participant meets the criterion of lost to follow up, no further direct efforts will be made to engage with that participant. As all participants will be participants of Enroll-HD, we will be able to obtain a proportion of 12-month assessment data for all participants unless they are lost to follow up in the Enroll-HD study. Remote data from FitBit activity monitors will also be collected from those lost to follow up.

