# 5.3 Primary outcomes measure(s)

The primary outcome measures for this trial are focused on feasibility of the 12-month physical activity intervention.

- Recruitment rate will be assessed using site recruitment logs.
- Retention rate will be measured as the percentage of individuals who completed the intervention.
- Adherence rates will be defined as percentage of intervention sessions completed,
- Safety will be assessed through monthly documentation completed by therapists administering the intervention, which captures information on falls history, medication

changes, healthcare service use and hospital admissions (classified as serious adverse events).

- Fidelity of the interventions will be assessed via review of coach documentation and activity monitor data.
- Data completeness will be assessed by the percentage of data entered into the database.

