# 11.3 Intervention comparator

#### Nested RCT

Those participants in the nested RCT randomised to activity as usual will not receive the physical activity intervention and will be asked to continue with their usual level of physical activity for the 12 month follow up period. They will not receive home visits from the intervention delivery staff (physical therapists), but they will be asked to record their activity monthly in paper diaries which will be sent to them. These participants will also receive monthly prompts via their preferred method of communication (e-mail/ telephone/ text messaging) to remind them to complete and return the diaries to their local coordinating centre in the stamped, addressed envelope provided. Their activity will not be monitored with the use of devices outside the week long activity monitoring period using Gene-activ devices that all participants will undertake.

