# 14.7 Inclusion in analysis

All participants enrolled into the cohort study will be included in the analysis of the cohort study results unless they specifically request to withdraw their data from analyses. Additionally, all participants randomised in the nested RCT will be included in the analysis of the RCT results unless they specifically request to withdraw their data.

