#### a. Feasibility

Summary data for recruitment, retention and data completeness will be tabulated for the cohort and nested RCT. Adherence rates, safety and fidelity will also be summarised for the RCT.

b. RCT

The individually randomised data from the three sites will be explored.

The analysis will compare

- I. Linked Enroll-HD data for participants between the two groups at 1 year
- II. PACE-HD trial data (see section 12.1)

Linear models will be used for key continuous outcomes, controlling for individual participant characteristics used to balance the randomisation as baseline covariates. Treatment effects will be summarised using regression coefficients, 95% confidence intervals and standardised effect sizes. Standard diagnostics will be performed to ensure adequate model fit (including inspecting fitted versus residual plots). The analysis will be intention to treat and complete case.

Analysis of secondary outcomes will proceed similarly, with linear regression used for continuous outcomes and logistic regression for dichotomous outcomes. A mediation analysis will be performed on the physical fitness measure recorded at 6 months. No inflation for clustering has been included in the power calculation however a sensitivity analysis will be conducted using hierarchical modelling to explore the extent of clustering in the primary outcome variable by site.

Progression criteria to proceed to further evaluation will be based on the following; over 60% drop out from the RCT at 12 months will mean no progression, between 40 and 60 % drop out will mean that changes to the intervention and/or follow-up procedures will be required and less than 30% drop at 12 months will indicate that the intervention is suitable for further evaluation without modification.

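### The nested RCT's loss-to-follow-up rule counts missed coaching, which only the intervention arm has, so PACE-HD-only outcomes can go missing selectively and drop-out has no common meaning across arms

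*Protocol*

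**What the plan says.** Protocol section 10.2 gives one definition for the nested RCT: "participants will be deemed to be lost to follow up if they fail to attend more than 4 consecutive coaching contact sessions". Once it is met, "no further direct efforts will be made to engage with that participant". The section then limits the damage: through Enroll-HD, "we will be able to obtain a proportion of 12-month assessment data for all participants", unless they are lost there too, and FitBit data continue to arrive.

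Section 11.1 gives the intervention arm 18 coaching sessions over 12 months. Under section 11.3 controls receive no intervention and no therapist home visits, only diaries and monthly prompts; Table 3 adds telephone reviews.

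Section 10.1 lists withdrawal from the intervention separately from partial or complete withdrawal from data collection, and asks that the two be clearly told apart. On analysis, section 14.7 says "all participants randomised in the nested RCT will be included in the analysis of the RCT results" unless they withdraw their data, and section 15.1 says "The analysis will be intention to treat and complete case".

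On feasibility, section 5.3 says "Retention rate will be measured as the percentage of individuals who completed the intervention". The progression rule in section 15.1 uses drop-out from the RCT by 12 months and does not define it. The process evaluation in section 12 says the team will try to contact people who drop out of the intervention, to learn why.

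**The concern.** Attendance at coaching measures adherence to one arm's treatment. Using it to declare people lost to follow-up merges two things that section 10.1 keeps apart, and does so in one arm only. If sites stop pursuing those participants, their PACE-HD assessments may never be made. The complete-case set for those outcomes would then hold intervention participants who kept some contact with their coach, set against controls who were never filtered in that way. That is not the comparison by randomised group that sections 14.7 and 15.1 intend.

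Non-attendance is plausibly related to outcome. Section 10.1 itself gives more frequent falls and worsening health as reasons for stopping the intervention.

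The primary objective is also touched. Feasibility is primary, and progression turns on a drop-out rate for which section 10.2 offers the only RCT definition of loss, one that half of the RCT cannot meet. This is a data-collection rule, so a statistical analysis plan could not recover assessments that were never sought.

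**Working it through.** **1. The plan's own figure.** Section 14.3 gives ±8.2% for 70% retention with n = 120. Check: 1.96 × √(0.70 × 0.30 / 120) = 0.082. It is reproduced, and nothing below changes it.

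**2. Who can meet the rule.** More than 4 consecutive misses means at least 5 of 18 sessions, or 5/18 = 28% of the programme. With even spacing that is 5/18 × 12 = 3.3 months. Even spacing is an assumption, because section 11.1 leaves timing to participant and coach. Controls have 0 sessions, so none can meet it.

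**3. Which outcomes are exposed** (section 12.1, Tables 1 to 3).
- Still obtainable at month 12 through Enroll-HD: total motor score, cognitive tests, functional scales, SF-12, mood scale, service use, Timed Up and Go, chair stand.
- PACE-HD only, month 12: predicted VO2max, 6-minute walk, GENEActiv, IPAQ, HD-PRO-TRIAD, Q-Motor, Q-Cog, Lorig scale.
- PACE-HD only, month 6: VO2max (the mediator in section 15.1), 6-minute walk (in Table 1), GENEActiv, IPAQ, C3T, Lorig scale. Enroll-HD visits are annual and cannot supply these.
- FitBit data exist in the intervention arm only, so they support no comparison between arms.

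**4. Possible bias for the PACE-HD-only outcomes.** Let L be the share of the intervention arm that meets the rule and has no outcome data, and g the amount in SD by which such people would do worse untreated. The protocol gives neither; L = 0.2-0.4 and g = 0.3-0.5 are assumptions. Suppose there is no true effect, controls contain the same mix of people, and set the mean of attender-type people to 0.
- Control mean = −L × g
- Intervention complete-case mean = 0
- Apparent benefit = L × g

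| L | Analysed (intervention v control) | g = 0.3 | g = 0.5 |
|---|---|---|---|
| 0.2 | 24 v 30 | 0.06 SD | 0.10 SD |
| 0.3 | 21 v 30 | 0.09 SD | 0.15 SD |
| 0.4 | 18 v 30 | 0.12 SD | 0.20 SD |

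The counts are 30 × (1 − L) against 30, before ordinary withdrawals in either arm. If g = 0 and there is no true effect, the bias is 0.

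**5. Progression rule.** Section 6 plans 30 v 30. Suppose drop-out were counted by the section 10.2 rule over all 60.
- 18 of 30 lost in the intervention arm (60%) gives 18/60 = 30%.
- 30 of 30 lost gives 30/60 = 50%.

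The stop at over 60% could not be reached by that rule alone.

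**The case against.** The strongest reply is that follow-up does not stop, and it largely stands. A reader might infer from section 10.2 that all data end once the rule is met. The section says otherwise: Enroll-HD month-12 data are kept, section 5.4 says most secondary measures come from that source, and section 15.1 lists linked Enroll-HD data first in the RCT comparison. Nor does section 10.2 bar assessing someone who attends. It ends efforts to engage, and sections 6 and 12.1 tie the supplementary measures to the Enroll-HD visit. Loss of the PACE-HD measures is therefore a likely result of following the text, not something it prescribes.

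Other stronger readings also fail:
- *Adherent intervention participants against all controls.* Someone who attends poorly but intermittently never triggers the rule, and controls can be missing through ordinary withdrawal. The one-sidedness belongs to this rule, not to all missing data.
- *A direct contradiction with section 9.4.* The statement there that "the participant will remain within the trial for the purpose of follow up and data analysis according to the treatment option" concerns an investigator who gives alternative treatment. It is an analogue, not the same case.
- *A flat contradiction with section 14.7.* Analysing people as randomised among those with observed outcomes is a common meaning of section 15.1's phrase. The fit is poor, but that alone is a limitation.
- *An effect inflated 1.25 to 1.67 times*, from 1/(1 − L) at L = 0.2 and 0.4. This needs non-attenders to gain nothing and all to lack data, yet they also have equipment, a FitBit and independent sessions.
- *A progression decision already determined by this rule.* Section 15.1 does not cite section 10.2. What is shown is that drop-out is undefined.

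Effect estimates are also exploratory, and section 14.3 plans no formal hypothesis tests. Intervention completion remains an intelligible measure for the intervention arm. None of this answers the core point: the definition fits one arm and conflates adherence with follow-up.

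**Conclusion.** The point holds in a limited form. Section 10.2 conflicts with the separation of withdrawal types in section 10.1 and sits badly with the intention-to-treat aim of sections 14.7 and 15.1. The exposure is confined to outcomes that only PACE-HD collects, all 6-month data, and the retention and drop-out measures. The possible bias of 0.06-0.20 SD under no true effect rests wholly on assumed values of L and g and on complete absence of data in those who meet the rule; the real size is unknown. The 50% ceiling follows from 30 v 30, but only if drop-out is counted by section 10.2 over both arms, which the protocol does not say. Because drop-out decides progression in a feasibility trial, its definition should be settled even though the effect estimates are exploratory.

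**What to change.** 1. In section 10.2, define RCT loss to follow-up identically in both arms as no month-12 assessment obtained. Record missed coaching only as non-adherence or withdrawal from the intervention.
2. State that every randomised participant who has not withdrawn from data collection is invited to the 6- and 12-month assessments whatever their coaching attendance, with month 12 alongside the Enroll-HD visit.
3. Use definition 1 for RCT retention (section 5.3) and for the progression rule (section 15.1). Report intervention completion separately, for the intervention arm only.
4. Align section 10.2 with the process evaluation in section 12 on contacting people who drop out.

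The cost is an amendment to sections 5.3, 10.2 and 15.1 and a few more assessments at visits already planned. Replacing the complete-case analysis with a repeated-measures model is optional: many outcomes have a single post-baseline value, and no model restores assessments that were never sought.
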